Notes: All ocular assessments are to be performed for both eyes unless noted otherwise. All assessments for a visit are to be performed on the same day, except those at screening. All study visits will be scheduled relative to the date of the Day 1 visit (first study treatment).

There must be a minimum of 21 days between study treatment visits occurring from the Day 1 visit through the Week 44 visit. If a site has an unexpected issue (e.g., the IxRS is not able to assign the study kit), a participant's randomization and first study treatment may be administered within 2 business days of the Day 1 visit assessments, after consultation with the Medical Monitor. The following assessments will be repeated on the day of randomization and study treatment administration: urine pregnancy test (if applicable), slit lamp examination, indirect ophthalmoscopy, pre-treatment IOP measurements (recorded on the Day 1 electronic case report form [eCRF] and dated accordingly), and any new concomitant medications.

^a Main Informed consent must be administered and documented before any study-specific screening procedure is performed and may be obtained more than 28 days before initiation of study treatment at the Day 1 visit. The Optional (RBR) Informed Consent Form for residual samples collection can be signed either at the screening or Day 1 visit prior to sample collection.

- d Body weight only.
- ^e For female participants only. If WOCBP, serum pregnancy test at screening and urine pregnancy test at the other visits.
- In study eye only.

Finger count vision assessment in study eye up to 15 minutes after study treatment or SoC administration.

Performed prior to pupil dilation.

[figure not shown]
m	In stud y eye only. The second study drug administration can only be given once IOP has returned to normal. If IOP ≥ 30 mmHg	at
	minutes after the second study drug administration, then IOP is measured again at 60 (±10) minutes.	
n		ı
		•
0	The study visit at Week 48 should not occur earlier than 28 days after the last study treatment.	

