P Early Treatment Termination (ETT) Visit; If a patient discontinues study treatment prior to Week 44, the ETT visit will be done (if consent still in place). If a decision to discontinue at Week 44 is taken, the regular Week 48 visit should be performed. Patients discontinuing from Study after Week 48 will perform the EOS visit (will be either Week 72 or earlier). Fundus Photography (UWF preferred), Fluorescein Angiography (UWF preferred) and OCT-A should be done if ETT visit ≥ 12 weeks after Day 1.

Legend: ; BCVA=best corrected visual acuity, D=Day, EC=Ethics Committee, ECG=electrocardiogram, EOS= End of study, ETT= early treatment termination, IOP=intraocular pressure, IxRS= interactive voice/web based response system; OCT-A= optical coherence tomography angiography, RBR= Roche Research Biosample Repository, SD-OCT=spectral domain optical coherence tomography, SoC= Standard of Care; UWF=Ultra-wide field, WOCBP=women of childbearing potential.

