4.4 END OF STUDY DEFINITION

A participant is considered to have completed the study if he/she has completed all phases of the study, including the End-of-Study (EOS) visit. The end of the study is defined as the date when the last participant, last observation (LPLO) occurs. LPLO is expected to occur at the EOS visit 4 weeks after the last participant has received SoC treatment in the off-treatment observation period or at Week 72 latest.

5. STUDY POPULATION

The study population consists of male and female participants of ≥ 18 years of age with DM (Type 1 or Type 2) and CI-DME who fulfill all of the inclusion criteria and none of the exclusion criteria.

The study population rationale is provided in Section 4.2.1.

Prospective approval of protocol deviations, also known as protocol waivers or exemptions, is not permitted.

One month is equivalent to a duration of 4 weeks (28 days).

RO7200220 and **RANIBIZUMAB—F. Hoffmann-La Roche Ltd** 38/Protocol BP43464, Version 3

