7.1 DISCONTINUATION OF STUDY TREATMENT

For data to be collected at the time of treatment discontinuation and follow-up and for any further evaluations that need to be completed see the SoA (Section 1.3).

Reasons for permanent discontinuation of study treatment (or withdrawal from the study) may include, but are not limited to, the following:

- Participant withdrawal of consent at any time.
- Any medical condition that the Investigator or Sponsor determines may jeopardize the participant's safety if he or she continues in the study.
- Investigator or Sponsor determination that treatment discontinuation is in the best interest of the participant.

Participants must discontinue study treatment if they experience any of the following:

- Pregnancy
- Retinal detachment or retinal tear in the study eye
- Vitreous hemorrhage that will preclude examination of the macula and obtaining adequate retinal imaging in the study eye

 Surgical intervention (i.e. vitreoretinal surgery, vitreous tap, or biopsy with IVT injection of anti-infectives or laser or retinal cryopexy with gas) to prevent permanent loss of sight

Every effort should be made to obtain information on participants who withdraw from the study but have not withdrawn consent. Participants who discontinue study treatment prematurely will be asked to return to the clinic for an ETTV (see Section 8.9.3) and may undergo follow–up safety assessments if required (see Section 8.9.4), unless the participant withdrew consent. The primary reason for premature study treatment discontinuation should be documented on the appropriate eCRF. Participants who discontinue study treatment prematurely will not be replaced.

For temporary interruption of study treatment see Section 6.6.1.

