8.3 ADVERSE EVENTS AND SERIOUS ADVERSE EVENTS

The definitions of AEs or SAEs can be found in Appendix 2. The non-serious adverse events of special interest (NSAESI), the sight-threatening AEs, and disease-related events and/or disease-related outcomes not qualifying as AEs or SAEs, are discussed in Sections 8.3.6, 8.3.7, and 8.3.8

The Investigator and any qualified designees are responsible for ensuring that all AEs

(including assessment of seriousness, severity and causality; see Appendix 2) are recorded on the Adverse Event eCRF and reported to the Sponsor in accordance with instructions provided in this section and in Appendix 2.

Procedures used for recording AEs are provided in Appendix 3:

- Diagnosis versus signs and symptoms
- AEs occurring secondary to other events
- Persistent or recurrent AEs
- Abnormal laboratory values
- Abnormal vital sign values
- Abnormal liver function tests
- Overdose (see also Section 8.4)
- Deaths
- Preexisting medical condition, including worsening of DME
- Worsening of disease (DME) being studied
- Hospitalization or prolonged hospitalization

8.3.1 Time Period and Frequency for Collecting Adverse Event and Serious Adverse Event Information

The method of recording, evaluating, and assessing causality of AEs and SAEs and the procedures for completing and transmitting SAE reports are provided in Appendix 2.

Investigators will seek information on AEs at each participant's contact. All AEs, whether reported by the participant or noted by study personnel, will be recorded in the participant's medical record and on the Adverse Event eCRF as follows:

After informed consent has been obtained **but prior to initiation of study treatment**, only SAEs caused by a protocol-mandated intervention should be reported (e.g., SAEs related to invasive procedures such as angiographies). Any other AE should not be reported.

After initiation of study treatment, all AEs, regardless of relationship to study treatment, will be reported until the final study visit (i.e. ETTV, EOS, or Week 72, whatever occurs first).

Post-study AEs and SAEs: The Investigator is not required to actively monitor participants for AEs after the end of the AE reporting period (i.e. ETTV, EOS, or Week 72, whatever occurs first).

However, if the Investigator learns of any SAE (including a death) or other AEs of concern that are believed to be related to prior treatment with study treatment, at any

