8.3.4.1 Emergency Medical Contacts

To ensure the safety of study participants, access to the Medical Monitors is available 24 hours a day 7 days a week. Details will be available separately.

8.3.5 Pregnancy

WOCBP will be instructed to immediately inform the Investigator if they become pregnant during the study, or within 12 weeks after the last dose of study treatment, or within 12 weeks after the dose of SoC, if applicable.

If a pregnancy is reported, the Investigator should inform the Sponsor within 24 hours of learning of the pregnancy and should follow the pregnancy reporting process as detailed in Appendix 5. All pregnancies reported during the study should be followed until pregnancy outcome, with follow-up information on the infant collected according to procedures outlined in Appendix 5.

Abnormal pregnancy outcomes (e.g., spontaneous abortion, fetal death, stillbirth, congenital anomalies, ectopic pregnancy) are considered SAEs (Appendix 5).

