Participants will return to the investigational site every 4 weeks up to Week 72 during the off-treatment observation period after their final dose of study drug at Week 44 for follow-up visits with assessments as outlined in the SoA (see Section 1.3) and in Section 4.1.1.

If during any of these visits the participants

for the EOS visit (see SoA in

Section 1.3). If the participants meet the criteria at Week 72 they would also receive a dose of SoC and the visit would become the EOS visit.

8.9.5 Assessments at the Occurrence of a Sight-Threatening Adverse Event or Events of Intraocular Inflammation

At the occurrence of sight-threatening AEs potentially linked to IMP (see Section 8.3.7 and Appendix 8) or events of intraocular inflammation (IOI), additional assessments are recommended to be done (if not anyway required at the visit) and will be reported in the eCRF:

- •
- Blood sample for laboratory safety analyses
- •
- Ophthalmological assessments including imaging

9. STATISTICAL CONSIDERATIONS

The primary efficacy endpoint is change in BCVA from baseline over the average of Weeks 44/48 in treatment naïve population. The estimated changes in the RO7200220 in combination with ranibizumab arm (Arm A), and the differences to the control arm

(Arm B) will be presented. No formal hypothesis testing will be performed. The BCVA endpoint will also be estimated in the previously treated population and in the overall population as secondary efficacy outcomes. SD-OCT measurements of CST are a key secondary endpoint.

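### Routine AE reporting closes at the early treatment termination visit, with no readable minimum time after the last dose, so new AEs are collected for a shorter post-dose period in early stoppers than in completers

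*Protocol*

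**What the plan says.** Protocol 8.3.1 requires all AEs after the first dose, whatever their cause, to be "reported until the final study visit (i.e. ETTV, EOS, or Week 72, whatever occurs first". Beyond that point, "The Investigator is not required to actively monitor participants for AEs after the end of the AE reporting period".

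The ETTV is triggered by stopping treatment. Note p to the Schedule of Activities (Protocol 1.3) reads: "If a patient discontinues study treatment prior to Week 44, the ETT visit will be done (if consent still in place". Protocol 7.1 agrees ("Participants who discontinue study treatment prematurely will be asked to return to the clinic for an ETTV") and adds that follow-up safety assessments under Section 8.9.4 are possible afterwards if needed. Protocol 8.9.3 instead describes the ETTV for participants withdrawn from the study.

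For those who complete treatment, note o to the schedule says: "The study visit at Week 48 should not occur earlier than 28 days after the last study treatment". Section 8.9.4 then provides: "Participants will return to the investigational site every 4 weeks up to Week 72 during the off-treatment observation period". Participation can end earlier once standard-of-care (SoC) treatment is given, since Section 4.4 says: "LPLO is expected to occur at the EOS visit 4 weeks after the last participant has received SoC treatment".

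On the analysis side, SAP 4.6.2 reports AEs as the proportion of participants affected in each arm. SAP 4.6 makes the final safety summaries cumulative to Week 72. SAP 4.6.1 tabulates average AE observation time but does not use it as a denominator.

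**The concern.** The rule ties the end of AE collection to a visit whose timing depends on when treatment stops. A participant who stops early leaves routine AE collection at the ETTV, while a completer stays in it for weeks or months after the last dose. Participants who must stop under Protocol 7.1 include those with retinal detachment or tear, or certain vitreous hemorrhages, so this is not a group in which safety information can be treated as unimportant.

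Two things are at stake. The first is capture. New events between the ETTV and the time a completer would have left the study are recorded only if they come to the investigator's notice and are believed related. This includes deaths: Appendix 3, Section 7 requires them to be recorded regardless of relationship only within the AE reporting period. The second is comparison. A proportion of participants with an event, pooled over unequal observation times, depends partly on how many stopped early in each arm.

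**Working it through.** The plan states no figure to reproduce, so the check is a reading of the text followed by visit arithmetic.

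**Is there a minimum interval from last dose to ETTV?** Schedule note p and Protocol 7.1 and 8.9.3 all describe the visit, and none gives one. The 28-day minimum in note o applies to Week 48 only. Participants who decide to stop at Week 44 have the regular Week 48 visit (note p), so the gap concerns stops before Week 44.

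**Does anything extend routine collection past the ETTV?**
- Protocol 7.1 allows later safety assessments, but Section 8.3.1 has by then closed reporting, so the status of a new AE found there is undefined.
- Protocol 8.3.3.1 follows recorded AEs until they resolve, stabilise or are explained. It does not collect new ones.
- Protocol 8.3.1 and Appendix 2, Section 5.1 keep a route for SAEs believed related; Section 8.3.1 also covers other related AEs of concern. Both depend on the investigator learning of the event.

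None of these is routine collection regardless of causality.

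**AE observation after the last dose** = week of AE cut-off − week of last dose, in nominal weeks and ignoring visit windows.
- Completer followed to Week 72: 72 − 44 = 28 weeks.
- Completer with the earliest end of study, taking SoC at Week 48 and the final visit 4 weeks later: 48 + 4 − 44 = 8 weeks.
- Early stopper: no documented value. Assuming an ETTV 0 to 4 weeks after the last dose, 0 to 4 weeks. The upper end is 4/28 = 14% of the longest completer window and 4/8 = 50% of the shortest.

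**Total AE observation if the ETTV falls at the next 4-weekly visit** = week of last dose + 4.

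| Last dose | AE observation (weeks) | Unobserved to Week 72 (72 − observed) | Unobserved to Week 52 (52 − observed) |
|---|---|---|---|
| Day 1 | 4 | 68 | 48 |
| Week 20 | 24 | 48 | 28 |
| Week 40 | 44 | 28 | 8 |

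**Effect on the comparison of arms.** Suppose AE risk over time is the same for everyone, so that only observation time differs. Let d be the share stopping early in an arm, and let p_c and p_e be the chances of a recorded AE in a completer and an early stopper, with p_e < p_c. The expected proportion is (1 − d)·p_c + d·p_e. The difference, Arm A minus Arm B, is −(d_A − d_B)·(p_c − p_e). It is zero when the arms stop equally and negative only if Arm A stops more. The documents give no value for d, p_c or p_e.

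**How many are affected?** This cannot be derived. The protocol plans 105 to 115 per arm for about 55 + 25 = 80 evaluable, and the SAP about 90 for the same 80. SAP 2.2 explains that the non-evaluable include participants who finished treatment under Protocol Version 1, so the gap is not a count of early stoppers.

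**The case against.** The best defence is that the important events are covered. A participant who stops for intraocular inflammation has that event recorded, followed to an outcome and updated in severity if it worsens (Appendix 3, Section 3), with extra assessments recommended under Protocol 8.9.5. Related SAEs and AEs of concern remain notifiable at any time. This stands, and it limits the loss to new events that are not believed related, not of concern, or never reported to the investigator. A reader might infer that every non-serious event and every unrelated SAE after the ETTV is lost; the documents do not support that.

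It can also be said that Sections 7.1 and 8.3.1 do not contradict each other, since optional visits to follow known AEs can coexist with an end to new-AE reporting. That is fair. Section 8.3.1 ties its cut-off to the final study visit and asks for AE information at every contact, so the fault is an unresolved question of whether the ETTV is final when further visits follow. Section 8.9.3 sharpens the question by describing the visit for study withdrawal rather than treatment discontinuation.

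Third, an interval of only a few days, which a reader might infer, has no documentary basis. Treatment visits must be at least 21 days apart, so a stop decided at the next dosing visit already gives about 3 weeks or more. This narrows the likely range but sets no floor, because an ETTV may be held between scheduled visits.

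Finally, some schedule notes and parts of Sections 4.1 and 8.9.4 are blacked out. A timing rule there cannot be excluded.

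**Conclusion.** The point holds in limited form. On the readable text, routine collection of new AEs ends at the ETTV for those who stop before Week 44, no minimum post-dose interval applies to them, and the status of AEs found at later safety visits is unsettled. Completers on the 44-week schedule have nominally 8 to 28 weeks after the last dose; early stoppers have 0 to 4 weeks under the stated assumption about ETTV timing, or longer if doses were missed before the decision to stop.

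Two further inferences should be resisted. One is that Arm A's AE incidence will be understated: this requires more stopping in Arm A, and the documents offer no evidence either way. SAP 4.6.1 would show unequal observation time, although nothing adjusts for it. The other is that the protocol already contains an AE window that was overlooked. The 28-day rule times the Week 48 visit, and the 12-week interval in Protocol 8.3.5 ("or within 12 weeks after the last dose of study treatment") governs pregnancy reporting. Neither was written for AEs, and they differ threefold (12 weeks against 4). They show that intervals counted from the last dose are familiar in this protocol, not which one should apply.

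**What to change.** Reconcile Protocol 7.1, 8.3.1 and 8.9.3. State that AE reporting runs to the participant's last study contact, including any safety visit after the ETTV, and in any case for a minimum interval after the last dose. The sponsor should choose and justify that interval. State also when the ETTV takes place relative to the last dose, and whether it applies to stopping treatment, leaving the study, or both.

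Carry the same window into SAP 4.6.2, and report exposure-adjusted AE rates beside the incidence proportions, using the AE observation time already tabulated under SAP 4.6.1. These rates account for unequal time at risk. They do not recover unrecorded events or remove bias if those who stop differ in risk, so they complement the protocol change and do not replace it.

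The cost is protocol wording, possibly one follow-up contact per early stopper who has not withdrawn consent, and one more column in the safety tables. The SAP rates need no new data collection.

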8.3.3.2 Sponsor Follow-Up

For SAEs, NSAESIs, and pregnancies, the Sponsor or a designee may follow up by telephone, fax, electronic mail, and/or a monitoring visit to obtain additional event details and outcome information (e.g., from hospital discharge summaries, consultant reports, autopsy reports) in order to perform an independent medical assessment of the reported event.

8.3.4 Regulatory Reporting Requirements for Serious Adverse Events

Immediate notification by the Investigator to the Sponsor of an SAE regardless of relationship to study drug is essential so that legal obligations and ethical responsibilities towards the safety of participants and the safety of a study treatment under clinical investigation are met.

The Sponsor has a legal responsibility to notify both the local regulatory authority and other regulatory agencies about the safety of a study treatment under clinical investigation. The Sponsor will comply with country-specific regulatory requirements relating to safety reporting to the regulatory authority, Institutional Review Boards (IRB)/Independent Ethics Committees (IEC), and investigators.

Investigator safety reports must be prepared for SUSARs according to local regulatory requirements and Sponsor policy and forwarded to investigators as necessary.

An Investigator who receives an Investigator safety report describing an SAE or other specific safety information (e.g., summary or listing of SAEs) from the Sponsor will review and then, file it along with the IB and will notify the IRB/IEC, if appropriate according to local requirements.

For immediate (i.e., no more than 24 hours after learning of the event) and expedited reporting requirements from Investigator to Sponsor and from Sponsor to Health Authority, investigators, IRB and EC, see Section 5 of Appendix 2.

8.3.4.1 Emergency Medical Contacts

To ensure the safety of study participants, access to the Medical Monitors is available 24 hours a day 7 days a week. Details will be available separately.

8.3.5 Pregnancy

WOCBP will be instructed to immediately inform the Investigator if they become pregnant during the study, or within 12 weeks after the last dose of study treatment, or within 12 weeks after the dose of SoC, if applicable.

If a pregnancy is reported, the Investigator should inform the Sponsor within 24 hours of learning of the pregnancy and should follow the pregnancy reporting process as detailed in Appendix 5. All pregnancies reported during the study should be followed until pregnancy outcome, with follow-up information on the infant collected according to procedures outlined in Appendix 5.

Abnormal pregnancy outcomes (e.g., spontaneous abortion, fetal death, stillbirth, congenital anomalies, ectopic pregnancy) are considered SAEs (Appendix 5).

8.3.6 Non-serious Adverse Events of Special Interest (immediately reportable to Roche)

Non-serious AEs of special interest are required to be reported by the Investigator to the Sponsor immediately (i.e., no more than 24 hours after learning of the event; see Appendix 2 for reporting instructions).

AEs of special interest (AESIs) for this study include the following:

- Cases of an elevated ALT or AST in combination with either an elevated bilirubin or clinical jaundice (as defined in Section 6 of Appendix 3).
- Suspected transmission of an infectious agent by the study treatment, as defined below:

Any organism, virus, or infectious particle (e.g., prion protein transmitting transmissible spongiform encephalopathy), pathogenic or non-pathogenic, is considered an infectious agent. A transmission of an infectious agent may be suspected from clinical symptoms or laboratory findings that indicate an infection in a participant exposed to a medicinal product. This term applies only when a contamination of the study treatment is suspected.

8.3.7 Sight-threatening Adverse Events (immediately reportable to Roche)

Sight-threatening AEs are defined in Appendix 8.

Sight-threatening AEs, regardless if considered serious or non-serious, are required to be reported by the Investigator to the Sponsor immediately (i.e., no more than 24 hours after learning of the event; see Appendix 2 for reporting instructions).

The follow-up actions for sight-threatening AEs are defined in Section 8.9.5.

8.3.8 Disease-Related Events and/or Disease-Related Outcomes Not Qualifying as Adverse Events or Serious Adverse Events

Not applicable.

